3.4. Safety endpoints

Safety endpoints will be:

- 1.3.4.1. Treatment-emergent adverse events and serious adverse events.
- 1.3.4.2. Treatment-emergent adverse events leading to premature discontinuation of study treatment.
- 1.3.4.3. Hypersensitivity reactions including anaphylactic/anaphylactoid reactions.
- 1.3.4.4. Treatment-emergent laboratory abnormalities
- 1.3.4.5. Assessment of immunogenicity.

4. STUDY DESIGN AND METHODS

4.1. Study design

This is a randomized, open-label, parallel-arm study to investigate the efficacy and safety of pamrevlumab in patients with documented SARS-CoV-2 infection. The study consists of screening, a treatment period, and a follow-up period.

The study will enroll patients who have been hospitalized and who are not currently on invasive mechanical ventilation. The treatment period is open ended, and patients will be randomized to treatment with pamrevlumab or standard of care in a 1:1 ratio according to a pre-generated randomization list. Pamrevlumab dosing, 30 mg/kg IV, will be administered at day 1, day 7 and day 14. Day 1 is defined as the day of randomization which must also include administration of the first dose of pamrevlumab for patients in the active treatment arm.

Based on Investigator's decision, treatment may be continued every 3 weeks after day 14, up to 11 weeks.

Since the treatment scheme of pamrevlumab for this study is more intense as compared to previous studies conducted in IPF patients, as a further safety measure the first 3 patients randomized to receive the experimental drug will be treated one at a time, leaving a 1-week observation period between them.

A follow-up by visit or phone call will be performed 8 and 12 weeks after the end of the last dose of treatment. The treatment period for an individual patient will not exceed 11 weeks. The end of the study is defined as last patient last follow-up visit/phone call.

The study design has a total sample size of approximately 68 patients and consists of two stages. At the end of Stage 1 (Stage 1 requires 23 patients on pamrevlumab treatment arm), analyses of efficacy and safety will take place with a potential to stop the study for futility or for efficacy. A data

review committee composed of experts in respiratory medicine and intensive care will be involved in study oversight and interpretation of the study results. In patients showing worsening of clinical condition, independently of the treatment arm, the Investigator is free to introduce any therapy considered necessary.

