3.2. Futility testing

Futility testing will be performed when 23 pamrevlumab patients completed 14 days of treatment. For futility testing of Stage 1 of the study, a responder rate definition will be evaluated. Patients randomized to receive pamrevlumab are considered responders if the total number of days on mechanical ventilation is ≤15 days after first dose of pamrevlumab and the patient is alive. In addition, chest high-resolution CT (HRCT) scans obtained at baseline and day 14 will used as supportive analyses in the assessment of futility. Such analyses will be based on both quantitative

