4.6. Determination of sample size

This study's sample size is based on Simon's two-stage design (Simon, 1989) on the pamrevlumab arm. For futility testing of Stage 1 of the study, a responder rate definition will be evaluated. Patients randomized to receive pamrevlumab are considered responders if the total number of days on ventilation is \leq 15 days after first dose of pamrevlumab and the patient is alive.

Key assumptions for sample size calculation include the following: (1) type I error rate, α (one-sided): 0.05; (2) power: 90%; (3) response probability of standard of care: 40%; (4) response probability of standard of care + pamrevlumab: 65%.

The null hypothesis that the true response rate is 40% will be tested against a one-sided alternative. In Stage 1, 23 patients will be accrued in pamrevlumab arm. If there are 9 or fewer responses in

these 23 patients, the study may be stopped. Otherwise, 11 additional patients will be accrued for a total of 34 in pamrevlumab treatment group. The null hypothesis will be rejected if 18 or more responses are observed in 34 patients on the pamrevlumab arm. This design yields a type I error rate of 0.05 and power of 90% when the true response rate is 65%.

The study will enroll approximately 50 patients in Stage 1 who will be randomized in 1:1 fashion (pamrevlumab vs. standard of care).

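### Section 4.1 allows an efficacy stop after Stage 1, but the Simon design in 4.6 has no efficacy boundary there, so its stated type I error was not computed for that stop

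*Protocol*

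**What the plan says.** Section 4.1 describes the end of Stage 1, which requires 23 patients on pamrevlumab, as the point where "analyses of efficacy and safety will take place with a potential to stop the study for futility or for efficacy". It names no test, threshold or share of the type I error for the efficacy side.

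Section 4.6 defines the design: "This study's sample size is based on Simon's two-stage design (Simon, 1989) on the pamrevlumab arm". The error rate is set as "type I error rate, α (one-sided): 0.05", and "The null hypothesis that the true response rate is 40% will be tested against a one-sided alternative". At Stage 1 there is one boundary, a lower one: with 9 or fewer responders among 23 the study may stop. With any higher count, 11 more patients join the pamrevlumab arm. The only rejection rule is at the end, at 18 or more of 34. Of this design the section says: "This design yields a type I error rate of 0.05 and power of 90" per cent when the true response rate is 65%.

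Section 3.2 describes the same look only as a test of futility: "For futility testing of Stage 1 of the study, a responder rate definition will be evaluated". Section 4.7 does likewise.

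**The concern.** Sections 4.1 and 4.6 describe different designs. Under 4.6, a trial with a very high Stage 1 response continues to 34 patients. Under 4.1, it may stop and claim success. An early success claim is a second opportunity to reject the null, and the stated error rate belongs to a design with only one.

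Without a fixed rule, the threshold for early success could be settled after the Stage 1 data are in. A positive conclusion could then rest on 23 pamrevlumab patients, or about 25 per arm, at a significance level that nobody has stated. It is also unclear whether the claim would use the single-arm comparison with 40% or a comparison between the randomised arms. The 4.6 calculation does not apply to the second at all.

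**Working it through.** **Inputs, all from section 4.6.** Null rate p0 = 0.40; alternative p1 = 0.65; one-sided type I error 0.05; power 90%; Stage 1 n1 = 23; futility at 9 or fewer; 11 further patients, 34 in total; final rejection at r = 18 or more.

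**Formula.** Let X1 ~ Bin(23, p) and X2 ~ Bin(11, p). With an efficacy stop at e or more of 23,

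P(reject) = P(X1 ≥ e) + Σ over x = 10 to e − 1 of P(X1 = x) · P(X2 ≥ r − x).

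Without an efficacy stop the first term vanishes and the sum runs to x = 23. The type I error uses p = 0.40 and the power p = 0.65.

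**Step 1: the plan's own figure, no efficacy stop.**
- r = 18, as written: type I error 0.0861, power 0.947. The stated 0.05 and 90% are not reproduced. Treating futility as non-binding changes little (0.0872).
- r = 19: type I error 0.0443, power 0.9002. This matches the stated figures, and 23/9/34 with this cut-off is the Simon minimax design for these inputs.

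The 18-versus-19 discrepancy is a separate error. Both cut-offs are carried below so that it is not charged to the efficacy stop.

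**Step 2: where an unadjusted Stage 1 test would reject.** At p = 0.40, P(X1 ≥ 13) = 0.0813, P(X1 ≥ 14) = 0.0349, P(X1 ≥ 15) = 0.0128 and P(X1 ≥ 16) = 0.0040. An exact one-sided 0.05 test with no allowance for the second look therefore rejects at 14 or more of 23.

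**Step 3: add the efficacy stop (type I error).**

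| Stage 1 efficacy stop | Final cut-off 19 of 34 | Final cut-off 18 of 34 (as written) |
|---|---|---|
| none | 0.0443 | 0.0861 |
| 14 or more | 0.0349 + 0.0242 = 0.0591 | 0.0349 + 0.0588 = 0.0938 |
| 15 or more | 0.0128 + 0.0345 = 0.0473 | 0.0128 + 0.0744 = 0.0872 |
| 16 or more | 0.0040 + 0.0407 = 0.0447 | 0.0040 + 0.0822 = 0.0862 |

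The increments at 14 of 23 are 0.0591 − 0.0443 = 0.015 and 0.0938 − 0.0861 = 0.008. A looser stop costs more: at 13 or more, the totals are 0.094 (cut-off 19) and 0.118 (cut-off 18). With cut-off 19, power is 0.903 for a stop at 15 and 0.901 for a stop at 16.

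**Step 4: if the efficacy stop compared the arms.** The protocol gives no level for such a test, so this step assumes one-sided 0.05 at both looks, 25 then 34 per arm, a 40% response in both arms, and no futility stop. A pooled z-test gives an overall type I error of about 0.078 (0.054 at the final look alone). Fisher's exact test gives 0.045.

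**The case against.** The strongest counter-argument is that 4.1 speaks only of a potential to stop, and that interim boundaries are often placed in an analysis plan or committee charter, neither of which is at hand. That answers a complaint that a boundary is missing. It does not answer the contradiction: 4.6 itself fixes a design with no early success and states its error rate, so an analysis plan that followed 4.6 would still conflict with 4.1.

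Several stronger readings are tempting but not supported.
- A reader might infer that the efficacy stop necessarily pushes the type I error above 0.05. No section says that Stage 1 would be tested at a nominal 0.05; the 14 of 23 cut-off is an assumption. With a final cut-off of 19, a stop at 15 or more stays below 0.05.
- A reader might attribute the whole 0.094 to the efficacy stop. Of that, 0.086 is already present without it.
- A reader might take 0.078 as the between-arm error. It comes from a z-test, which the protocol does not name. Section 4.7 names Fisher's exact test or the Cochran-Mantel-Haenszel test for categorical endpoints, and Fisher's shows no excess over 0.05. An unstratified Cochran-Mantel-Haenszel test would behave much like the z-test, so inflation there is possible but not established.
- A reader might infer from the open label that accumulating results are seen by everyone. The protocol mentions a data review committee (4.1) and a safety board (section 7), and does not say who sees pooled data.

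**Conclusion.** The inconsistency stands: 4.1 permits an early efficacy stop, while 4.6 (with 3.2 and 4.7) describes a Stage 1 look at futility only. The stated type I error was not computed for the efficacy stop, and its control cannot be verified from the protocol.

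The size depends on choices the protocol leaves open. Under the single-arm rule with an unadjusted Stage 1 cut-off, the stop adds about 0.015 when the final cut-off is 19, enough to cross 0.05, and about 0.008 when it is 18, where 0.05 is already exceeded. A strict boundary adds almost nothing. These figures assume p0 = 0.40 and that the futility rule is followed. Confidence is high in the contradiction and lower in any single magnitude. It should be corrected, because it decides what the trial may conclude after Stage 1.

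**What to change.** The simplest change is to delete the efficacy alternative (the last three words of the 4.1 clause quoted above), so that Stage 1 is futility only, as in 3.2, 4.6 and 4.7.

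If an early success claim is wanted, state in 4.6 which test it uses and its Stage 1 boundary, and restate the exact type I error and power. One single-arm example is 16 or more of 23 with 19 or more of 34: type I error 0.045, power 0.90. A boundary of 15 of 23 would also hold (0.047, power 0.903). If the claim is to compare the arms, name the test and its level at each look, since the single-arm calculation does not carry over.

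Deleting the words does not by itself bring the error rate to 0.05: under the written 18 of 34 it stays at 0.086, and that cut-off must be corrected separately.

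The cost is three words removed or one sentence added. The downside is that an early success claim is given up or made harder to reach.

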4.2. Number of subjects

The study will enroll approximately 68 patients. The study will first enroll approximately 50 patients in Stage 1 and may continue to enroll more patients after review of Stage 1 data.

4.3. Diagnosis and main criteria for inclusion

Eligible patients are those with documented COVID-19, age \geq 18 to \leq 80 years with interstitial pneumonia (findings of consolidation or ground glass opacities as assessed by chest HRCT) and respiratory distress, defined as PaO₂/FiO₂ ratio of \geq 100 \leq 300 mmHg, requiring supplemental oxygen and hospitalization.

Exclusion criteria for the study are the following:

- Invasive mechanical ventilation at screening;
- Pregnancy;
- Incapacity to express a valid informed consent;
- Known hypersensitivity to monoclonal antibodies used as experimental drugs for any clinical indication.

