4.5. Concomitant and prohibited therapy

Patients previously treated with tocilizumab can be enrolled in the study, if considered not benefitting from the treatment, in the opinion of the Investigator.

Concomitant use of IL-1 inhibitors (e.g., anakira, canakinumab), TNF inhibitors, JAK inhibitors, and chloroquine/hydroxychloroquine is not allowed. If any of these therapies are initiated at the discretion of the Investigator (e.g., as rescue therapy due to worsening of the patient's condition), then the patient should be withdrawn from study.

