4.7. Statistical methods

For futility testing in Stage 1, a responder rate definition will be used. Patients randomized to receive pamrevlumab are considered responders if the total number of days on ventilation is \leq 15 days after the first dose of pamrevlumab. In addition, chest HRCT scans obtained at enrollment and day 14 \pm 2 will used as supportive analyses in the assessment of futility.

Analysis of continuous endpoints will be conducted using analysis of covariance (ANCOVA) model with baseline value as a covariate and relevant baseline prognostic factors as other covariates.

Analysis of categorical endpoints will be conducted using either Fishers Exact test or Cochran-Mantel-Haenszel test comparing the categories between the two treatment arms.

Analysis of the time to mechanical ventilation, time to all-cause mortality, and time to hospital discharge, respectively, will be undertaken by plotting Kaplan-Meier curves. Hazard ratios will be estimated using the Cox proportional hazards model and these will be presented together with 95% two-sided confidence intervals. Other statistical methods will be applied, as appropriate.

5. Subject withdrawal criteria

Subjects may withdraw from the study at any time, for any reason. Reasons for discontinuing study drug treatment, as well as reasons for withdrawing from study, will be captured on CRF.

Reasons for withdrawing the subject from the study may include the following:

- 5.1. Any safety concern in the Investigator's opinion, that precludes further study participation
- 5.2. Pregnancy
- 5.3. Withdrawal of Consent

6. Pamrevlumab: storage, preparation and use

Pamrevlumab is a fully human IgG1 kappa monoclonal antibody that binds to CTGF and is formulated as solution for administration by IV infusion.

Pamrevlumab is supplied in single-use glass vials containing sterile, preservative-free solution 10 mg/ml pamrevlumab. The solution is composed of 10 mg/mL pamrevlumab, 1.60 mg/mL L-histidine, 3.08 mg/mL L-histidine HCl, 8.01 mg/mL sodium chloride, and 0.05 mg/mL polysorbate 20, resulting in a solution with a tonicity of approximately 290 mmol/kg and a pH of 6.0.

Vials of pamrevlumab must be stored refrigerated (2°C to 8°C), in a temperature- controlled and monitored environment, protected from light, and in a securely locked area to which access is limited to appropriate study personnel. Documentation of the storage conditions must be maintained.

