The following attributes must be assigned to each AE:

- 7.1. Description (Investigator's verbatim term describing the event)
- 7.2. Dates of onset and resolution
- 7.3. Severity
- 7.4. Relationship to study drug
- 7.5. Outcome
- 7.6. Action taken regarding study drug
- 7.7. Other treatment required
- 7.8. Determination of "seriousness"

To date over 600 patients are exposed to pamrevlumab, few with IPF up to five years, and others for more than 4 years with non-ambulatory Duchenne Muscular Dystrophy. As of to-date, no treatment-emergent serious adverse events of allergic or anaphylactic reactions were observed. However, the study drug will be stopped and study terminated if signs of serious allergic reactions are observed.

Blood-samples to determine immunogenicity: human-anti-human antibodies (HAHAs) will be collected prior to first dose, at regular intervals: days 7 and 14 during treatment, as well as at the last visit, 12 weeks after the end of treatment, as part of safety analyses.

8. Data collection, handling, and verification

Source documents are original documents, data, and records necessary for the reconstruction and evaluation of the clinical study. All required data will be entered onto source documents by authorized site personnel and all data including lab reports will be provided to FibroGen to be entered into a validated, clinical database compliant with 21 CFR Part 11 regulations.

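### The only allergy exclusion (Section 4.3) is limited to antibodies used experimentally, so known hypersensitivity to a marketed antibody in approved use, or to a formulation component, does not literally exclude a patient

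*Protocol*

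**What the plan says.** Section 4.3 introduces its list with "Exclusion criteria for the study are the following" and gives four items: invasive mechanical ventilation, pregnancy, inability to consent, and "Known hypersensitivity to monoclonal antibodies used as experimental drugs for any clinical indication". There is no item on the components of the study drug and none that leaves exclusion to the investigator's judgement.

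Four other parts of the protocol bear on the scope of that last item:

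- Section 3.4 names hypersensitivity reactions, including anaphylactic and anaphylactoid reactions, as one of five safety endpoints.
- Section 4.5 states: "Patients previously treated with tocilizumab can be enrolled in the study, if considered not benefitting from the treatment, in the opinion of the Investigator". Lack of benefit is the only condition; tolerance is not mentioned.
- Section 6 gives the composition of the solution besides the antibody: "1.60 mg/mL L-histidine, 3.08 mg/mL L-histidine HCl, 8.01 mg/mL sodium chloride, and 0.05 mg/mL polysorbate 20". It also sets a rule for the individual patient: after a hypersensitivity or anaphylactic reaction the infusion stops, and that patient receives no further treatment and is followed for safety.
- Section 7 reports no serious allergic or anaphylactic event in more than 600 exposed patients and then adds: "However, the study drug will be stopped and study terminated if signs of serious allergic reactions are observed".

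**The concern.** The criterion does not cover all monoclonal antibodies. It covers those used experimentally. An investigator who applies it as written may enrol a patient whose known reaction was to a licensed antibody given for its licensed purpose, or to an ingredient of the study drug. The protocol looks for allergic reactions during and after infusion, counts them as a safety endpoint, and attaches a consequence for the study to serious ones. It does not consistently use the information about allergy that is available before the first dose.

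Two things are at stake. The first is the safety of a patient whose history was known at screening. The second is consistent application: two investigators could decide differently about the same patient, depending on what each counts as experimental use. Because Day 1 is both randomization and first dose (Section 4.1), a doubt raised only at the bedside would concern a patient already allocated to a pamrevlumab arm planned at 34.

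**Working it through.** The protocol states no figure on this point, so there is nothing to reproduce. The check is a reading of the entry criteria, followed by a test of whether the size can be estimated.

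**Step 1: who is caught by the Section 4.3 wording.**

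| Known prior hypersensitivity to | Excluded on the literal wording? |
|---|---|
| Pamrevlumab itself, or another antibody given as an experimental drug | Yes |
| A marketed antibody given off-label or experimentally | Arguably yes; depends on how the qualifier is read |
| A marketed antibody in its approved use | No |
| A listed component (L-histidine, L-histidine HCl, sodium chloride, polysorbate 20) | No |

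**Step 2: whether anything else closes the last two rows.**

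- The other three exclusions and the inclusion criteria in Section 4.3 do not concern allergy.
- Section 4.5 restricts certain concomitant drugs, not allergic history.
- The investigator's safety judgement appears in Section 5 (item 5.1), but as a reason for withdrawal, which applies after enrolment.
- The schedule in Section 9 has a medical history at screening, so the information would be collected, but no exclusion acts on it.
- The staggering of the first three treated patients (Section 4.1), the slower first infusions and the observation (Section 6) act at or after dosing.

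Nothing in the document closes the gap before enrolment.

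**Step 3: whether the gap can be sized.** The documents give neither the share of candidates with such a history nor their risk of reacting to pamrevlumab. As an assumption only, let a share q of candidates have such a history, with q between 0.5% and 2%. Section 4.6 plans n = 34 on pamrevlumab.

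- Expected number enrolled = n × q: 34 × 0.005 = 0.17, and 34 × 0.02 = 0.68.
- Chance of enrolling at least one = 1 − (1 − q)^34: 1 − 0.995^34 = 15.7%, and 1 − 0.98^34 = 49.7%.

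These figures describe enrolling such a patient, not a reaction. A second unknown is needed for that. If, again purely as an assumption, 10% of such patients reacted seriously, the expected number of reactions would be 0.1 × 0.17 = 0.017 to 0.1 × 0.68 = 0.068.

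The experience in Section 7 does not supply the missing rate. Zero events in 600 gives a one-sided 95% upper bound of 1 − 0.05^(1/600) = 0.50%, but that applies to exposed patients overall. The protocol does not say how many of them had a prior antibody or component allergy.

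**The case against.** The strongest reply is that the wording is broader than it first looks. The qualifier may describe how an antibody was used and not whether it is licensed. On that reading it covers off-label and experimental use of marketed products as well as pamrevlumab itself. This stands, and it narrows the gap to marketed antibodies in approved use and to the formulation components. It may also be a drafting slip for all monoclonal antibodies, which would be a reason to correct the text.

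A reader might infer from Section 4.5 that patients who reacted to tocilizumab are knowingly let in. The document does not support that. The section is silent on allergy, and if tocilizumab was given experimentally for COVID-19, which the protocol does not say, a reactor is already excluded. What remains is that the answer depends on interpretation.

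A reader might also infer that one reaction in such a patient would end the trial. Section 7 sets no case count, but it speaks of reactions in the plural, and Section 6 describes an action for the individual patient only. Whether a single case ends the study is unclear. That tension would exist whatever Section 4.3 said.

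It is also fair to say that no passage identifies any listed component as an allergic risk, that the protocol does not rank hypersensitivity above its other safety endpoints, and that the safeguards at infusion are substantial. Those safeguards limit harm once dosing has begun; they do not decide who is enrolled.

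**Conclusion.** The point holds in a limited form. On its literal wording, the only allergy criterion leaves out two groups whose history could be known at screening, and no other entry rule covers them. This sits badly with a named safety endpoint, with the admission of patients previously given another antibody, and with the study-level language in Section 7.

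The practical size is probably very small and cannot be quantified from the documents; the ranges above rest entirely on assumed rates. Two further inferences are unsupported: that a reaction in such a patient would distort the safety conclusion, and that the trial as a whole would be lost. The conclusion rests on reading the four exclusions as the complete list, which is how Section 4.3 presents them. It is worth correcting as an inexpensive improvement in patient safety and clarity.

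**What to change.** The sponsor should reconcile the scope of the Section 4.3 criterion with Sections 3.4, 4.5, 6 and 7. Two edits to Section 4.3 would do this:

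- Remove the qualifier on experimental use, or keep it and give the reason.
- State whether known hypersensitivity to other monoclonal antibodies, including previously given tocilizumab, and to the components listed in Section 6 falls within the criterion.

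The patient-level rule in Section 6 and the study-level sentence in Section 7 must also be reconciled, so that it is clear what a single serious reaction entails. Which clinical rule applies is for the sponsor and the investigators to decide.

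The cost is a line or two of eligibility text and a clarification in Sections 6 and 7. The Section 4.3 edits change no dose, schedule, endpoint or sample size. The downside is at most a few more screen failures, identified from the medical history that Section 9 already requires at screening.
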